7.1 Background and Demographic Characteristics, Variables measured during treatment

Inclusion/Exclusion criteria/Eligibility criteria: Frequencies of "Does the patient meet all inclusion and none of the exclusion criteria according to the protocol?" (yes/no). Frequencies of (yes/no) for each inclusion and exclusion criteria.

Type of Lymphoma/MYD88 mutation: Frequencies for Type of lymphoma (MALT lymphoma/splenic MZL/nodal MZL), extranodal MZL expression (extragastric/gastric), PD-L1 expression in lymphoma cells (negative/positive/not done) and MYD88 mutation (negative/positive/not done). The variables *LYMTYPE*, *TOLEX_EXGA*, *MYDMUT*, and *TOLP_DEX* in table *TOL* will be used.

Demographic characteristics: Demographic characteristics are age, sex, childbearing potential, and ethnic origin. For the analysis, the variables *AGE*, *SEX*, *RPORRES*, *CETHNIC*, and *ETHNICOTH* in table *DM* will be used.

Medical / Surgical History and Concomitant Diseases: Previous and concomitant diseases will be listed (name of disease, grade, start date, ongoing at the end of study, stop date).

Anamnesis and Status of Tumor: Frequencies of patients with previous rituximab/chemotherapy / rituximab single agent therapy / radiotherapy, Number and median of previous treatments in total and number of previous rituximab/chemotherapies / rituximab single agent therapies / radiotherapies will be calculated (variables *MHTHERAP*, *MHTHERAPN* in table *MH2*). The kind of therapy incl. start date, stop date, best response and duration of best response will be listed. The respective variables are *MHTHERKN*, *MHTSRT*, *MHTSTP*, *MHTHRESP*, *MHRESPDUR* and *MHTHERKN_x*, *MHTSRT_x*, *MHTSTP_x*, *MHTHRESP_x*, *MHRESPDUR_x*, $x=2, 3, 4, 5$ in table *MH2*. Frequencies for LDH value above the upper limit and Ann Arbor staging (I, II, III, IV) will be calculated. The respective variables are *MHLDHV* and *MHSTAGE* in table *MH2*. The MALT-IPI score will be evaluated as continuous variable (variable *MHMSCORE* in table *MH2*); only in patients with MALT lymphoma. An additional variable *MZLIPI* will be calculated as follows: if $MHMSCORE=0$ then $MZLIPI='Low (LRG)'$, if $MHMSCORE$ in $(1\ 2)$ then $MZLIPI='Intermediate (IRG)'$, if $MHMSCORE \geq 3$ then $MZLIPI='High (HRG)'$.

B Symptoms: The frequency for B-symptoms (yes/no) and the frequencies (yes/no) for Fever, Night sweats, Unintentional weight loss, and other relevant symptoms will be calculated. In case of other relevant symptoms, the symptoms will be listed. The respective variables are *FAYN*, *FEV_FAORRES*, *NS_FAORRES*, *WL_FAORRES*, *FAOTHYN*, and *FAOTHSPY* in table *FA*.

Hematology: The frequency of "Examination performed?" (yes/no) will be calculated. Parameters of hematology are hemoglobin, hematocrit, platelets, erythrocytes, leukocytes, neutrophils, and lymphocytes. The respective variables are *HGB_LBORRES*, *HCT_LBORRES*, *PLAT_LBORRES*, *RBC_LBORRES*, *WBC_LBORRES*, *NEUT_LBORRES*, and *LYM_LBORRES* in table *LBHM*.

Furthermore, for each of the parameter the frequency for 'clinically significant' (yes/no) will be calculated. Other cells examined will be listed.

Serum chemistry: The frequency of "Examination performed?" (yes/no) will be calculated. Parameters of serum chemistry are potassium, LDH, ALT, AST, GGT, alkaline phosphatase, uric acid, and CRP. The respective variables are *K_LBORRES*, *LDH_LBORRES*, *ALT_LBORRES*, *AST_LBORRES*, *GGT_LBORRES*, *ALPH_LBORRES*, *URIC_LBORRES*, and *CRP_LBORRES* in table *LBCC*. Furthermore, for each of the parameter the frequency for 'clinically significant' (yes/no) will be calculated.

Serum protein electrophoresis (SPEP) / immunofixation in serum (IF): For serum protein electrophoresis the frequency of "Examination performed?" (yes/no) will be calculated. The quantity will be analyzed for albumin, alpha1, alpha2, beta, and gamma (variables *SPEP_ALBU_ORRES*, *SPEP_ALPI_ORRES*, *SPEP_ALPII_ORRES*, *SPEP_BETA_ORRES*, and *SPEP_GAMMA_ORRES* in table *LBSIS*). Furthermore, the test result (M-protein in SPEP) and the absolute and relative quantity will be analyzed (variables *SPEP_LBORRES*, *SPEPQ_LBORRES*, and *SPEPQ_LBORRES2* in table *LBSIS*). For immunofixation in serum the frequency of "Examination performed?" (yes/no) will be calculated. The result of M-protein in IF and the specifications will be analyzed (variables *IF_LBPERF*, *IF_LBORRES*, *IF_LBTEST*, and *IFS_LBORRES* in table *LBSIS*).

Serology: Frequencies for the result (negative/positive) for HIV, HBsAg, HBcAb, HBV-DNA, HBsAb, HCV, and HCV-RNA will be calculated. The respective variables are *HIV_LBORRES*, *HBSAG_LBORRES*, *HBCAB_LBORRES*, *HBVD_LBORRES*, *HBSAB_LBORRES*, *HCV_LBORRES*, and *HCVRND_LBORRES* in table *LBSER*.

Peripheral blood -/ Leukocyte Immunophenotyping (FACS) – Antigen expression of the lymphoma: Frequencies for "FACS analysis performed?" (yes/no) and "Positive for malignant lymphoma cells?" (yes/no) will be calculated (variables *LBPBPERF* and *LBPBCAT* in table *LBPB*). Furthermore, and the kappa-result, lambda-result, and kappa / lambda ratio – result will be analysed. The respective variables are *KAPPALC_LBORRES*, *LMBDLC_LBORRES*, and *KLCLLC_LBORRES* in table *LBPB*).

Quantitative Immunoglobulins: Frequencies for "Examination performed?" (yes/no) will be calculated (variable *QIM_LBPERF* in table *LBIMG*). The results for IgA, IgG, and IgM will be analysed (variables *IGA_LBORRES*, *IGG_LBORRES*, and *IGM_LBORRES* in table *LBIMG*).

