For extranodal marginal zone lymphoma of mucosa-associated lymphoid tissue (MALT) a prognostic index was built by Cox regression, using data from 401 patients enrolled in the international randomized International Extranodal Lymphoma Study Group 19 (IELSG-19) trial. A validation set, including 633 patients, was obtained by merging 3 independent cohorts of MALT lymphoma patients. The 3 individual features maintaining the greatest prognostic significance for event-free survival (EFS, the main endpoint of the IELSG-19 trial) were age > 70 years (hazard ratio [HR], 1.72; 95% confidence interval [CI], 1.26-2.33), Ann Arbor stage III or IV (HR, 1.79; 95% CI, 1.35-2.38), and an elevated lactate dehydrogenase level (HR, 1.87; 95% CI, 1.27-2.77). The prognostic index (MALT-IPI) constructed using these 3 parameters identified 3 groups: low, intermediate, and high risk (corresponding to the presence of 0, 1, or ≥ 2 of these factors, respectively). The 5-year EFS rates in the low-, intermediate-, and high-risk groups were 70%, 56%, and 29%, respectively. The MALT-lymphoma International Prognostic Index (MALT-IPI) also significantly discriminated between patients with different progression-free, overall, and cause-specific survival. The prognostic utility was retained in gastric and nongastric lymphomas, in each treatment arm (chlorambucil, Rituximab, and Rituximab plus chlorambucil), and was confirmed in the validation set ¹⁹.

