In patients with gastric extranodal MZL, the initial staging should include a gastroduodenal endoscopy with multiple biopsies from the stomach, duodenum, gastroesophageal junction, and any site that seems abnormal and must not be older than 12 weeks before start of treatment. If any disease sites are identified in this manner at screening, a subsequent gastroduodenal endoscopy and biopsy are required to confirm a CR. In addition, if other sites are involved at baseline, they should be appropriately staged at baseline and re-evaluated during follow-up. For response evaluation endoscopy should be performed at C10D1 and at the end of treatment. H. pylori status must be evaluated. Endoscopic ultrasound to evaluate the regional lymph nodes and gastric wall infiltration should be performed.

In patients with non-gastric extranodal MZL, the initial staging should be adapted to the affected site as follows and according to local practice:

- Small intestine (immunoproliferative small intestinal disease, IPSID): Campylobacter Jejuni search in the tumor biopsy by polymerase chain reaction (PCR), immunohistochemistry or in situ hybridization may be carried out.
- Large intestine: colonoscopy.
- Lung: Bronchoscopy + bronchoalveolar lavage.
- Salivary glands: Ear/nose/throat examination and ultrasound. To eliminate association with Sjögren syndrome anti-SSA or anti-SSB antibodies should be investigated.
- Thyroid: echography ± computer tomography (CT) scan of the neck and thyroid function tests.
- Ocular adnexa: MRI (or CT scan) and ophthalmologic examination. Chlamydia psittaci in the tumor biopsy and blood mononuclear cells by PCR may be considered.
- Breast: mammography and MRI (or CT scan).
- Skin: Borrelia Burgdorferi in the tumor biopsy by PCR (in endemic areas) may be considered.

For all patients with extranodal MZL the MALT-IPI should be determined. It is the decision of the investigator to conduct a FDG-PET-CT. Investigations must not be older than 12 weeks before start of treatment. If any disease sites are identified in this manner at screening, a subsequent investigation is required to confirm a CR. For response evaluation investigations should be performed at C10D1 and at the end of treatment.

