The estimated duration of 12-18 months for patient recruitment on which the study design was based during initial planning has been exceeded substantially. The trial was stopped after inclusion of 22 (MALT lymphoma: n=8, splenic MZL: n=7, nodal MZL: n=7) of 56 planned patients since the initiation of the first site in Aug 2021. Additionally, eight patients not fulfilling the inclusion criteria had signed the ICF. The end of treatment visit of the last patient enrolled was 06 Dec 2024. Patients were included in Germany in 9 of 12 activated trial sites.

Further information about the trial is in the study protocol (V-3.0, 12 Apr 2021). Figure 1 shows the study design (see also CTP, page 33).

Fig.1: Study Design

POLE-1

Pembrolizumab in Marginal Zone Lymphoma

A multicenter open-label single-arm phase II study

Figure 1: POLE-1 study design. The Follow-Up phase follows after the treatment phase.

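### SAP 7.1 groups the MALT-IPI score as 0 / 1–2 / ≥3, which does not match the index's 0 / 1 / ≥2 grouping in protocol 4.1; either the cut-offs or the input variable is wrong (minor, descriptive only)

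*SAP*

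**What the plan says.** Protocol 4.1 describes the MALT-IPI as built from age above 70 years, Ann Arbor stage III or IV, and elevated LDH: "The prognostic index (MALT-IPI) constructed using these 3 parameters identified 3 groups". The groups are "low, intermediate, and high risk (corresponding to the presence of 0, 1, or ≥ 2 of these factors, respectively". Protocol 9.1.2 asks for the index at staging: "For all patients with extranodal MZL the MALT-IPI should be determined".

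SAP 7.1, under the anamnesis and tumour status item, first deals with the score itself: "The MALT-IPI score will be evaluated as continuous variable (variable *MHMSCORE* in table *MH2*); only in patients with MALT lymphoma". It then adds a derived variable, MZLIPI, whose only input is MHMSCORE. Score 0 is labelled low, scores 1 and 2 are combined ("then $MZLIPI='Intermediate (IRG"), and the last branch is "if $MHMSCORE \geq 3$ then $MZLIPI='High (HRG".

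SAP section 3 lists the changes to the planned analyses and says that no further deviations from the protocol are known. It does not mention the risk grouping.

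**The concern.** A count of three factors runs from 0 to 3, so on this score a cut-off of ≥3 can only mean exactly 3. The SAP keeps its high-risk label for patients with all three factors, whereas the protocol's account of the index gives that label to patients with two or three. The same score of 2 is therefore high risk in one document and intermediate in the other.

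What is at stake is the accuracy of a reported baseline table. The two groups differ in prognosis by the protocol's own figures: "The 5-year EFS rates in the low-, intermediate-, and high-risk groups were 70%, 56%, and 29%, respectively". A reader who sees an intermediate/high split for the MALT patients would naturally take it as the published MALT-IPI split, and under the SAP rule it would not be.

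**Working it through.** The check is on category cut-offs, so there is no power or sample-size figure to reproduce.

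**Inputs**

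- Number of factors: 3 (protocol 4.1), so the score is 0, 1, 2 or 3.
- Grouping of the index: 0 / 1 / ≥2 (protocol 4.1).
- Grouping in the SAP: 0 / 1–2 / ≥3 (SAP 7.1).
- Patients to whom the score applies: those with MALT lymphoma, 8 of 22 enrolled (SAP 2.1: "MALT lymphoma: n=8, splenic MZL: n=7, nodal MZL: n=7").

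**Both rules applied to every possible score.** Three yes/no factors give 2³ = 8 combinations.

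| Score | Combinations | Protocol 4.1 | SAP 7.1 | Same? |
|---|---|---|---|---|
| 0 | 1 | Low | Low | yes |
| 1 | 3 | Intermediate | Intermediate | yes |
| 2 | 3 | High | Intermediate | **no** |
| 3 | 1 | High | High | yes |

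Only score 2 changes group. The high group falls from 3 + 1 = 4 combinations to 1. These counts describe the rule; they are not expected patient frequencies.

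**Size in this trial.** The number of MALT patients with score 2 is not given, so between 0 and 8 could be affected. Each one moves 1/8 = 12.5 percentage points of the MALT group from high to intermediate.

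**Can the correct groups be recovered?** Yes. The raw score stays in the data. It can also be worked out from the planned output. Let N be the number of patients with a score, m the mean score, I the count labelled intermediate and H the count labelled high by the SAP. Write n1, n2 and n3 for the numbers with scores 1, 2 and 3.

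- N × m = n1 + 2·n2 + 3·n3
- I = n1 + n2, and H = n3
- so n2 = N × m − I − 3·H

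The correct high group is then H + n2, and the correct intermediate group is I − n2.

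**Where the SAP split could come from.** Protocol 4.1 does contain a 0 / 1–2 / 3–4 grouping, but for a splenic MZL score with up to four factors. That score uses haemoglobin and platelet cut points, and the study it follows on from also names LDH and extrahilar lymphadenopathy. Those cut-offs do not carry over to a count of age, stage and LDH in MALT patients. Whether the SAP split was taken from there cannot be settled from the documents.

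**The case against.** The strongest reply is that MZLIPI may not be meant as the MALT-IPI risk group. It has its own name and labels, is introduced as an additional variable, and has a top category that would suit an index with more than three factors. The annotated CRF that defines MHMSCORE is not among the documents. This stands as a reason not to assert that the cut-offs are the faulty part. It does not rescue the rule: neither document defines another index under that name, and the sole input is the score that the SAP itself calls the MALT-IPI. If another index is meant, the input is wrong instead.

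A second reply is that protocol 4.1 is background reporting a published index, and that protocol section 12 prescribes no MALT-IPI grouping for analysis. That is correct, so the SAP does not breach a protocol analysis rule. Section 4.1 is still the only MALT-IPI grouping in either document, and the SAP gives no reason to depart from it.

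A third reply is that little depends on the variable. This also stands. MZLIPI enters no primary, secondary, safety or sensitivity analysis. The exploratory logistic regressions on risk factors, where it might have been used, were dropped (SAP section 3). Age, LDH above the upper limit, Ann Arbor stage and the raw score are all reported alongside it, and SAP 8.1 displays single values where there are too few measurements.

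A reader might infer something stronger: that the rule makes the MALT patients look lower risk and so distorts the comparison of the trial's CR rate with a historical MALT rate. The documents do not support this. The planned test compares the whole MZL population with 56%, and no MALT-specific comparison is planned. Protocol 4.1 ties the risk groups to event-free, progression-free, overall and cause-specific survival and gives no CR rate by group. The documents do not report the risk mix of the historical rituximab arm either. Any downward shift also needs at least one patient with score 2, and there may be none.

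**Conclusion.** The inconsistency is real. SAP 7.1 applies cut-offs to the MALT-IPI score that do not belong to that index as the protocol describes it, and either the cut-offs or the input variable must be wrong. Followed as written, the SAP labels every MALT patient with exactly two factors intermediate instead of high risk; this is 0 to 8 of 8 patients.

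The conclusion rests on MHMSCORE being the three-factor MALT-IPI count, as the SAP says, and on protocol 4.1 describing the index correctly. It does not depend on which of the two errors was made.

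Severity is minor. The effect is limited to a descriptive baseline variable in at most 8 patients. It does not touch the primary test or any secondary endpoint, and it is reversible from the raw score. It is not evidence that the CR rate or its comparison with 56% is biased.

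**What to change.** State in SAP 7.1 which index MZLIPI represents, then do one of the following:

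- If it is the MALT-IPI risk group, define it as low for score 0, intermediate for 1 and high for ≥2, and rename it so that the name matches the index.
- If it is another index, name it, list its factors and cut-offs, and derive it from those factors in the patients to whom it applies, not from MHMSCORE.

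In either case, show the frequency of each raw score (0, 1, 2, 3) in the MALT patients, so that the grouping can be checked in the table itself. The cost is one line of SAP text and the matching line of code. No new data are needed and no other analysis changes.

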7.2 Variables measured during Follow-Up

Variables measured during Follow-Up cover the following: ECOG Performance Status, B symptoms, hematology, serum chemistry, urine analysis, HBV DNA PCR, new anti-lymphoma treatment, survival follow-up, CT/MRI scan and tumor assessment (if initially positive), leukocyte immunophenotyping (FACS), quantitative immunoglobulins (IgA, IgG, IgM), serum protein immunofixation (if positive before), bone marrow aspirate and biopsy, and QoL questionnaire (FACT-Lym). Details are mentioned in part 7.1, see above. Patients with disease progression will be followed for new anti-lymphoma treatment and survival twice per year until the end of the study. Patients, who have not progressed so far, will be observed according to the follow up schedule in the CTP.

7.3 End of treatment

For evaluation of the end of treatment, the frequencies (yes/no) for the question "Was study medication in treatment period applied?" will be calculated. The date of last application and the reason (variables *EXENDAT_ET* and *EXREASND_ET* in table *DSET*) will be listed. Additionally, the frequencies for the primary reasons for termination will be calculated and listed (variable *DSDECOD_ET* in table *DSET*). The specifications for termination and the date of progression and

the date will be listed (variables *DSAESPY_ET* and *RSDAT_ET* in table *DSET*). Additionally, the date of last contact and the specification will be listed (variables *DSLSTDAT_ET* and *DSTERM_ET* in table *DSET*). Furthermore, the frequency of specification (Refusal of further study treatment/Withdrawal of consent) and status of patient (Patient continues with follow-up/Patient discontinues study) will be calculated (variables *DSDECOD_ET2* and *DSCONT_ET* in table *DSET*).

7.4 End of Study

For evaluation of the end of study, the primary reasons for termination will be calculated and listed and the specifications will be listed (variables *DSDECOD_EST*, *DSSF_EST*, and *DSAESPY_EST* in table *DSEOS*). The date and specification of last contact will be listed (variables *DSLSTDAT_EST* and *DSTERM_EST* in table *DSEOS*). The frequencies (yes/no) for the question "Is the patient still alive?" will be calculated. The date and cause of death and will be listed. The frequencies for the cause of death (tumor-related/adverse event/other) will be calculated. The variables are *SURVSTAT*, *DTHDAT*, *PRCDTH_DDORRES*, and *DSAESP_EST* in table *DSEOS*.

- e) Progression free survival (PFS)
- f) Time to treatment failure (TTF)
- g) Duration of Response (DR)
- h) Cause specific survival (CSS)
- i) Overall survival (OS)
- j) Quality of life during trial (therapy)

Details for a): The response rates (complete response (CR), partial response (PR) and overall response rate (OR (CR or PR))) are evaluated 4 weeks after the end of treatment at point in time EOT/ET visit C18/D1. The complete response CR is therefore identical with the primary endpoint (see above). For the analysis of the response rates and the overall response rate, the variables *RSORRES_NMZEG* (nodal MZL and extragastric MALT lymphoma), *RSORRES_EGM* (extranodal gastric MALT lymphoma) and *RSORRES_SMZ* (splenic MZL) in table *RS* for the variable *ACTIVITY_ID* = 'EOT_ASS' will be used. The single categories for the response rates are CR, PR, SD, PD, and NE and will be defined using the categories in the database/CRF as follows:

- CR: nodal MZL and extragastric MALT lymphoma: CR; extranodal gastric MALT lymphoma: CR/pMRD; splenic MZL: CR
- PR: nodal MZL and extragastric MALT lymphoma: PR; extranodal gastric MALT lymphoma: PR/rRD; splenic MZL: PR
- SD: nodal MZL and extragastric MALT lymphoma: SD; extranodal gastric MALT lymphoma: SD / NC; splenic MZL: SD / No Response
- PD: nodal MZL and extragastric MALT lymphoma: PD; extranodal gastric MALT lymphoma: PD; splenic MZL: PD
- NE: nodal MZL and extragastric MALT lymphoma: NE; extranodal gastric MALT lymphoma: NE; splenic MZL: NE

For analysis, a new variable *ASS_RESULT* will be calculated as follows:

- nodal MZL and extragastric MALT lymphoma:
 - IF *RSORRES_NMZEG* = 1 THEN *ASS_RESULT* = 1;*CR;
 - IF *RSORRES_NMZEG* = 2 THEN *ASS_RESULT* = 2;*PR;
 - IF *RSORRES_NMZEG* = 3 THEN *ASS_RESULT* = 3;*SD;
 - IF *RSORRES_NMZEG* = 4 THEN *ASS_RESULT* = 4;*PD;
 - IF *RSORRES_NMZEG* = 5 THEN *ASS_RESULT* = 5;*missing;
- extranodal gastric MALT lymphoma
 - IF *RSORRES_EGM* = 1 THEN *ASS_RESULT* = 1;*CR;
 - IF *RSORRES_EGM* = 2 THEN *ASS_RESULT* = 2;*PR;
 - IF *RSORRES_EGM* = 3 THEN *ASS_RESULT* = 3;*SD;
 - IF *RSORRES_EGM* in (4 5) THEN *ASS_RESULT* = 4;*PD;
 - IF *RSORRES_EGM* = 6 THEN *ASS_RESULT* = 5;*missing value;
- splenic MZL:
 - IF *RSORRES_SMZ* = 1 THEN *ASS_RESULT* = 1;*CR;
 - IF *RSORRES_SMZ* = 2 THEN *ASS_RESULT* = 2;*PR;
 - IF *RSORRES_SMZ* = 3 THEN *ASS_RESULT* = 3;*SD;
 - IF *RSORRES_SMZ* = 4 THEN *ASS_RESULT* = 4;*PD;
 - IF *RSORRES_SMZ* = 5 THEN *ASS_RESULT* = 5;*missing value;

For the analysis of the overall response rate (CR or PR), a new variable *ORR* (yes/no) will be calculated from the variable *ASS_RESULT* as follows: IF *ASS_RESULT* in (1 2) THEN *ORR* = 1; ELSE *ORR* = 0;

Absolute and relative frequencies will be calculated for the statistical analysis of the variables *ASS_RESULT* and *ORR*.

Details for b): Best response (CR, PR, SD, PD) is determined in the time interval from the start of therapy to end of follow-up. At first, the single categories for the analysis of the response rates (CR, PR, SD, PD, NE) will be defined and calculated as described in section 'Details for a)' (see above) for each point in time in which a tumor assessment was performed and a new variable *THERAPY_RESULT* will be created. The best response for a patient is the minimum (i.e. the best outcome) of the variable *THERAPY_RESULT*, measured across all points in time with tumor assessment (over the entire observation time). The result is stored in a new variable *BEST_RESPONSE*.

Details for c): Time to best response is defined as the time from the start of therapy to best response the patient achieves (CR, PR). For calculation, the difference between the date of the first day of treatment in cycle 1 (*C1/D1*; see CTP pages 106-110) (variable *EXSTDAT* for *ACTIVITYID* = '*C1D1_SV*' in table **EX1**) and the date of best response (i.e. first date at which CR is reached; in case of no CR is reached, the first date at which PR is reached) will be used. For the determination, the variable *THERAPY_RESULT* (see section 'Details for b)' above) will be used, together with the date of assessment which is calculated as variable *ASS_DATE* from the variables *RSDAT_NMZEG*, *RSDAT_EGM* and *RSDAT_SMZ* in table **RS**. Patients who reach CR or PR: The earliest date at which CR or PR is documented will be determined for each patient across all points in time with tumor assessment and will be used as end date for time to best response (not censored). Patients who do not achieve the response category CR or PR, will be censored at the latest tumor assessment date.

Details for d): Time to first response is defined as the time from the start of therapy to first response (CR, PR). For calculation, the difference between the date of the first day of treatment in cycle 1 (*C1/D1*; see CTP pages 106-110) (variable *EXSTDAT* for *ACTIVITYID* = '*C1D1_SV*' in table **EX1**) and the date of first response (first date at which CR or PR is reached) will be used. For the determination, the variable *THERAPY_RESULT* (see section 'Details for b)' above) will be used, together with the date of assessment which is calculated as variable *ASS_DATE* from the variables *RSDAT_NMZEG*, *RSDAT_EGM* and *RSDAT_SMZ* in table **RS**. Patients who reach CR or PR: The earliest date at which CR or PR is documented will be determined for each patient across all points in time with tumor assessment and will be used as end date for time to first response (not censored). Patients who do not achieve the response category CR or PR, will be censored at the latest tumor assessment date.

Details for e): Progression free survival is defined as the time of registration to the first occurrence of progression or relapse as assessed by the investigator, or death from any cause. PFS for patients without disease progression, relapse, or death will be censored at the time of the last tumor assessment. Progression free survival will be calculated as difference between time of registration (date of patient signed written informed consent; variable *RFICDAT* in table **DM**) and the earliest date of the event (progression or relapse or death) or the date of last tumor assessment (in case of no event). For the earliest date in case of progression or relapse the dates in table **RS** will be used as follows: nodal MZL and extragastric MALT lymphoma: variable *RSDAT_NMZEG* for *RSORRES_NMZEG* = 4, extranodal gastric MALT lymphoma: variable *RSDAT_EGM* for *RSORRES_EGM* in (4 5), splenic MZL: variable *RSDAT_SMZ* for *RSORRES_SMZ* = 4. Additionally for the date of progression, the variable *RSDAT_ET* (table **DSET** IF *DSDECOD_ET* = 3) will be used for identifying patients with PD. For patients who died, the date of death will be determined using the variable *DTHDAT* in table **DSEOS**.

Details for f): Time to treatment failure is defined as the time of registration to discontinuation of therapy for any reason including death from any cause, progression, toxicity or add-on of new anti-cancer therapy. Time to treatment failure will be calculated as difference between time of registration (date of patient signed written informed consent; variable *RFICDAT* in table *DM*) and the earliest date of the event (discontinuation of therapy for any reason). The following information will be used for the determination of the last mentioned date:

- discontinuation of therapy for any reason: variable *EXENDATE_ET* in table *DSET* for *DSDECOD_ET* not in (1 3).
- death from any cause: the date of death will be determined using the variable *DTHDAT* in table *DSEOS*
- progression: the dates in table *RS* will be used as follows: nodal MZL and extragastric MALT lymphoma: variable *RSDAT_NMZEG* for *RSORRES_NMZEG* = 4, extranodal gastric MALT lymphoma: variable *RSDAT_EGM* for *RSORRES_EGM* in (4 5), splenic MZL: variable *RSDAT_SMZ* for *RSORRES_SMZ* = 4. Additionally for the date of progression, the variable *RSDAT_ET* (table *DSET* for *DSDECOD_ET* = 3) will be used for identifying patients with PD.
- end of treatment: variable *RSDAT_ET* for *DSDECOD_ET* = 3 in table *DSET*
- death: variable *DTHDAT* for *DSDECOD_EST* = 4 in table *DSEOS*
- add-on of new anti-cancer therapy: variable *PRSTDAT* in table *PR2* for the first event in a patient

Patients alive without treatment failure are censored at the latest tumor assessment date.

Details for g): Duration of Response will be calculated in patients with response to therapy (CR, PR) from diagnosis of response to the date of progression, relapse or death from any cause. It will be calculated as difference between date of diagnosis of response and the earliest event date (progression, relapse or death from any cause). The date of diagnosis of response will be determined as variable *ASS_DAT* from the variables *RSDAT_NMZEG* (nodal MZL and extragastric MALT lymphoma), *RSDAT_EGM* (extranodal gastric MALT lymphoma) and *RSDAT_SMZ* (splenic MZL) in table *RS* for the variable *ACTIVITY_ID* = 'EOT_ASS' and *ASS_RESULT* in (1 2) (see section 'Details for a') above).

For the determination of the earliest event date, the following information will be used:

- progression and relapse: For the date in case of progression or relapse the data in the tables *RS*, *DSET*, and *DSEOS* will be used as described in section 'Details for e)', see above
- death from any cause: For patients who died, the date of death will be determined using the variable *DTHDAT* in table *DSEOS*

In case of an event is the event date for remission duration the earliest date among these dates. Patients alive without progression and relapse will be censored at the latest tumor assessment date or the stopping date.

Details for h): Cause specific survival is defined as the period from the study registration to death from lymphoma or lymphoma related cause; death unrelated to MZL is considered as a competing event. CSS will be calculated as difference between time of registration (date of patient signed written informed consent; variable *RFICDAT* in table *DM*) and the date of an event (variable *DTHDAT* for *SURVSTAT* = 0 and *PRCDTH_DDORRES* = 1 in table *DSEOS*). Patients who have not died or died from another reason than lymphoma or lymphoma related cause until the time of the analysis will be censored at their last contact date.

Details for i): Overall survival is defined as the period from the registration to death from any cause. Overall survival will be calculated as difference between time of registration (date of patient signed written informed consent; variable *RFICDAT* in table *DM*) and the date of death (variable *DTHDAT*

for *SURVSTAT* = 0 in table *DSEOS*). Patients who have not died until the time of the analysis will be censored at their last contact date.

Details for j): Quality of life was measured by the FACT Lym before start of treatment and during trial participation. For statistical analysis, the FACT-Lymphoma Trial Outcome Index (TOI), the FACT-G total score, the FACT-Lymphoma total score and the sum score for each of the five subscales (physical well-being (PWB), social/family well-being (SWB), emotional well-being (EWB), functional well-being (FWB), lymphoma subscale (LYMS)), will be calculated. Details about the calculations are provided in two separate documents doc01_Administration Guidelines_Manual_082505.pdf and doc19_ScoringFACT-Lym v4-REVISED.pdf.

